8.3.3 Exclusion Criteria

Subjects will be excluded from the study if one or more of the following criteria is applicable:

1. Current diagnosis of a major depressive episode, or lifetime diagnosis of attention-deficit/hyperactivity disorder, bipolar disorder, psychotic depression, schizophrenia or other psychotic disorder, feeding and/or eating disorder, obsessive-compulsive disorder, conduct disorder, oppositional defiant disorder, post-traumatic stress disorder, panic disorder, or pervasive development disorder.
2. Suspected or previously diagnosed intellectual disability disorder.
3. DSM-5-defined substance use disorder within a year (12 months) prior to Screening Visit.
4. Any secondary DSM-5 disorder that requires pharmacologic treatment or would be a potential confound to the study assessments or ability to participate in all study procedures, as determined by the investigator.
5. Environmental stressor (current or historic – eg, history of abuse/trauma, significant change in psychosocial status, significant injury) that, in the opinion of the investigator, may confound assessments or subject's ability to complete all protocol requirements.
6. One or more first-degree relatives with diagnosed bipolar I disorder.
7. Subject answers “yes” to “Suicidal Ideation” item 3 (active suicidal ideation with any methods, not plan, without intent to act), item 4 (active suicidal ideation with some intent to act, without specific plan), or item 5 (active suicidal ideation with specific plan and intent) within the past 6 months and/or a lifetime history of suicidal behavior, as assessed by the C-SSRS.
8. Subject is currently considered at risk for suicide in the opinion of the investigator.
9. Lack of response to 2 or more adequate trials of antidepressants or other anti-anxiety medications at a clinically appropriate dose for a minimum of 4 weeks for GAD at the time of screening or, in the judgement of the investigator, the patient had treatment-resistant GAD.
10. Change to psychotherapy (start, stop, or change in type, intensity, or frequency) in the 6 weeks prior to the Screening Visit.
11. History of seizure disorder (other than febrile seizures).

CONFIDENTIAL

12. History of electroconvulsive therapy at any time during the subject's lifetime.
13. Had a positive urine drug screen for any substances of abuse or excluded medication.

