10.1.2 Safety Assessments

10.1.2.1 Columbia-Suicide Severity Rating Scale

The C-SSRS is an instrument designed to systematically assess and track suicidal ideation and behavior¹⁵. The strength of this suicide classification system is in its ability to comprehensively identify suicidal events while limiting the over-identification of suicidal behavior.

The C-SSRS will be completed by the investigator or appropriately qualified study center staff and the scores recorded on the eCRF. Every effort should be made to ensure that the assessments are completed by the same assessor at each visit.

Any positive score should be reported to the medical director and immediate subject care should be implemented and documented. Any positive score should be recorded as an AE or SAE, as appropriate.

In addition to the planned assessments, the investigator must continually evaluate suicidality risk throughout the subject's participation in the study.

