Possible: Clinical event with a reasonable time relationship to study drug administration, but that could also be explained by concurrent disease or other drugs or chemicals.

Probable: Clinical event with a reasonable time relationship to study drug administration, and is unlikely to be attributed to concurrent disease or other drugs or chemicals.

Very Likely/Certain: Clinical event with plausible time relationship to study drug administration, and that cannot be explained by concurrent disease or other drugs or chemicals.

Action Taken

The investigator will describe the action taken in the appropriate section of the eCRF, as follows:

- None
- Study drug stopped

CONFIDENTIAL

- Study drug temporarily interrupted
- Concomitant medication
- Other, specify.

Follow-up of Adverse Events

All investigators should follow up subjects with AEs until the event is resolved or until, in the opinion of the investigator, the event is stabilized or determined to be chronic. Details of AE resolution must be documented in the eCRF.

Documentation and Reporting of Adverse Events

All AEs from the signing of the informed consent form (ICF) until 30 days after receiving the last dose of study drug will be collected according to the procedures outlined above at the timepoints specified in the Schedule of Assessments ([Section 8.1.2/8.1.3](#)), and as observed or reported spontaneously by study participants.

AEs should be reported and documented in accordance with the procedures outlined below. All AEs occurring during the study must be documented on the relevant eCRF pages. The following data should be documented for each AE:

- Description of the symptom event
- Classification of 'serious' or 'not serious'
- Severity
- Date of first occurrence and date of resolution (if applicable)
- Action taken
- Causal relationship
- Outcome of event (unknown, recovered, recovering, not yet recovered, recovered with sequelae, death [with date and cause reported]).

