11.6 Safety Analysis

The safety analysis will be performed for the double-blind treatment period and double-blind down taper period separately using the Safety Population. The safety parameters will include AEs, clinical laboratory parameters, vital sign measurements, and ECG parameters. For each safety parameter, the last assessment made before the first dose of double-blind investigational product will be used as the baseline for all analyses of that safety parameter.

Safety data collected outside of planned visit windows but within allowance limits (up to 1 week late for Visits 7 and 8) will be included in the summary tables. Safety data collected outside of planned visit windows and outside of the allowance limits (>1 week to 6 weeks late for Visits 7 and 8) will be listed, but will not be included in the summary tables. Subgroup analyses may be performed to assess the impact of COVID-19 on the safety analyses.

The safety endpoints during the double-blind treatment period are as follows:

- Incidence of treatment-emergent adverse events (TEAEs).
- Observed values and change from baseline in vital signs (blood pressure, pulse rate, temperature, respiration rate, height, weight, BMI, height percentile, weight percentile, and BMI percentile); incidence of vital sign potentially clinically significant (PCS) values.
- Observed values and changes from baseline in ECG intervals and interpretation; incidence of ECG PCS values.
- Observed values and changes from baseline in clinical laboratory assessments (hematology, chemistry, and urinalysis); incidence of clinical laboratory PCS values.
- Incidence of suicidal ideation and/or suicidal behavior as determined by the C-SSRS.

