9.2.8 Analysis of COVID-19 impact assessment score

The global COVID-19 impact assessment will be used to evaluate the impact of the coronavirus disease pandemic on the severity of the subject's GAD during the last 1 week. The rating will include scores from 0 (not applicable, subject not enrolled in the trial during the pandemic) to 7 (extreme impact). Raters will also evaluate whether the impact was an improvement or worsening of the subject's GAD.

Subjects with scores from 4 (moderate impact) to 7 (extreme impact) at any visit other than the Screening Visit will be considered to have been significantly impacted, regardless of the direction of impact.

Number and percentage of subjects with each score on the global COVID-19 impact assessment will be summarized descriptively at each visit by treatment group for the mITT population, including subjects that were significantly impacted. For each score from 2 to 7, the number and percentage of subjects who improved or worsened will also be summarized.

Page 29 of 53

Page 30 of 53

10.0 SAFETY ANALYSES

The safety analysis will be performed for the double-blind acute treatment period and the double-blind down-taper period separately, using the Safety Population unless stated otherwise.

The safety parameters include adverse events (AEs), clinical laboratory parameters, vital signs, electrocardiographic (ECG) parameters, and suicide risk assessment using the Columbia-Suicide Severity Rating Scale (C-SSRS). For each safety parameter, the last non-missing safety assessment before the first dose of double-blind investigational product will be used as baseline. Continuous variables will be summarized by number of subjects and mean, SD, median, minimum, and maximum values. Categorical variables will be summarized by number and percentage of subjects.

Safety data collected outside of planned visit windows but within allowance limits (up to 1 week late for Visits 7 and 8) will be included in the summary tables. Safety data collected outside of planned visit windows and outside of the allowance limits (>1 week to 6 weeks late for Visits 7 and 8) will be listed, but will not be included in the summary tables. Subgroup analyses may be performed to assess the impact of COVID-19 on the safety analyses; details are listed in each safety section.

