10.1 ADVERSE EVENTS

Adverse events will be coded by SOC and PT using the MedDRA version 22.0 or newer.

An AE (classified by PT) that occurs during the double-blind acute treatment period, during the down-taper period, or within 30 days after the date of the last dose of double-blind investigational product will be considered a treatment-emergent adverse event (TEAE) if it was not present before the date of the first dose of double-blind investigational product, or was present before the date of the first dose of double-blind investigational product and increased in severity during the double-blind acute treatment period or during the down-taper period, respectively.

If more than 1 AE was reported before the date of the first dose of double-blind investigational product and coded to the same preferred term, the AE with the greatest severity will be used as the benchmark for comparison with the AEs occurring during the double-blind acute treatment period or during the down-taper period that were also coded to that preferred term. An AE that occurs more than 30 days after the date of the last dose of double-blind investigational product in the study will not be counted as a TEAE but will be included in the listings.

Page 31 of 53

An AE occurring during the down-taper period or safety follow-up period will be considered a newly emergent AE (NEAE) if it is not present before the start of the down-taper period or was present before the start of the down-taper period but increased in severity during the down-taper period. All NEAEs will be summarized by SOC, PT, and treatment group.

The number and percentage of subjects in each treatment group reporting TEAEs during the double-blind acute treatment period will be tabulated by SOC and PT; by SOC, PT, and severity; and by SOC, PT, and causal relationship to the investigational product. If more than one AE is coded to the same PT for the same subject, the subject will be counted only once for that PT using the most severe and most related occurrence for the summarization by severity and by causal relationship to the investigational product, respectively. Study-treatment-related TEAEs are defined as TEAEs with relationship to treatment categorized as Possible, Probable, Very, Like/Certain or missing.

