10.5 COLUMBIA-SUICIDE SEVERITY RATING SCALE

For the C-SSRS, the number and percentage of subjects with any suicidal ideation or suicidal behavior will be presented by treatment group, separately for the lifetime history, the double-blind acute treatment period and the double-blind down-taper period. The distribution of responses for the most severe suicidal ideation and suicidal behavior will be summarized by treatment group, separately for the lifetime history, the double-blind acute treatment period, and the double-blind down-taper period. Supportive listings will be provided and will include the SID number, treatment group, visit number, lifetime history, and postbaseline values for each subject. Intensity of ideation, suicidal behavior type, and lethality of suicidal behavior will also be included in these listings.

SAP SCT-MD-60 Allergan

Page 37 of 53

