16.3 REPEATED OR UNSCHEDULED ASSESSMENTS OF SAFETY PARAMETERS

If a subject has repeated assessments before the date of first dose of double-blind investigational product, the results from the final nonmissing assessment made before the date of the first dose of double-blind investigational product will be used as baseline. If end-of-double-blind-treatment period assessments are repeated or if unscheduled visits occur, the last nonmissing post-baseline assessment during the double-blind acute treatment period will be used as the end-of-double-blind-acute-treatment-period assessment for generating summary statistics. Likewise, if end of double-blind down-taper period assessment during the double-blind down-taper period will be used as the end-of-double-blind-down-taper-period assessment for generating summary statistics.

Similarly, if a subject has repeated assessments within a given visit window, the last non-missing post-baseline assessment during the window will be used as the assessment for that visit window when generating summary statistics.

However, all post-baseline assessments will be used to determine PCS values for laboratory parameters, vital signs and ECG parameters, and to determine most severe suicidal ideation and most severe suicidal behavior from C-SSRS. All assessments will be presented in the data listings.

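### SAP 10.5 counts any on-treatment suicidal ideation without using the pre-dose C-SSRS, so low-level ideation carried in from entry is counted the same as a new case

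*SAP*

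**What the plan says.** The protocol's safety endpoint (11.6) is "Incidence of suicidal ideation and/or suicidal behavior as determined by the C-SSRS", with no new-or-worsened qualifier. SAP 10.5 turns this into by-arm counts: "the number and percentage of subjects with any suicidal ideation or suicidal behavior will be presented by treatment group, separately for the lifetime history", then the acute treatment and down-taper periods. It adds the distribution of the worst category in each period and subject listings. SAP 16.3 uses all post-baseline assessments "to determine most severe suicidal ideation and most severe suicidal behavior from C-SSRS". That is a worst value, not a change.

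A reference point exists. The C-SSRS is scheduled at Screening and Baseline (protocol 8.1.2). The opening of SAP section 10.0 lists it among the safety parameters and states: "For each safety parameter, the last non-missing safety assessment before the first dose of double-blind investigational product will be used as baseline". SAP 10.5 makes no use of this.

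Exclusion 7 (protocol 8.3.3) bars ideation items 3 to 5 "within the past 6 months and/or a lifetime history of suicidal behavior, as assessed by the C-SSRS". Items 1-2 are not named.

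On the adverse event side, protocol 10.1.2.1 says "Any positive score should be recorded as an AE or SAE, as appropriate". Protocol 10.1.2.2 says "All AEs from the signing of the informed consent form (ICF) until 30 days after receiving the last dose of study drug will be collected". Under SAP 10.1, when more than one pre-dose event has the same preferred term, "the AE with the greatest severity will be used as the benchmark for comparison" with on-treatment events of that term.

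**The concern.** Protocol 8.2.1 gives increased suicidality under antidepressants as the reason for repeating the C-SSRS at every visit. The table meant to show this mixes two kinds of subject: those whose ideation began or worsened on treatment, and those who came in with passive ideation and still have it. The lifetime-history row cannot separate them, because it pools remote with current ideation.

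The plan treats other safety data differently. Rates of potentially clinically significant laboratory and ECG values require a baseline that was not already abnormal in that sense (SAP 10.2, 10.4). Laboratory values and ECG interpretation also get shift tables. Ideation gets neither. A reader of the final table could see two similar percentages and not know whether they conceal a difference in new cases.

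**Working it through.** **1. Who can enter with ideation.** By exclusion 7:

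- Any lifetime suicidal behavior: barred, so on-treatment behavior is new apart from eligibility deviations.
- Items 3-5 within 6 months: barred. Items 3-5 seen on treatment are new relative to that window, and the worst-category distribution shows them apart from items 1-2.
- Items 1-2 now: not barred by this criterion. Exclusion 1 (current major depressive episode) and exclusion 8 (investigator's view of suicide risk) will remove some of these children, but not by a rule on items 1-2.

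The gap is therefore mainly items 1-2.

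**2. Size of the dilution.** The documents give no C-SSRS rate, so there is no planned figure to reproduce and every rate here is an assumption. Let c be the share in each arm whose entry ideation persists, and p the new-onset rate in the rest. The tabulated 'any' rate is c + (1 - c)p. The risk difference is (1 - c) times the true difference. With p = 2% (placebo) and 6% (escitalopram):

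| c | Placebo | Escitalopram | Ratio | Difference (points) |
|---|---|---|---|---|
| 0% | 2.00% | 6.00% | 3.00 | 4.00 |
| 2% | 3.96% | 7.88% | 1.99 | 3.92 |
| 5% | 6.90% | 10.70% | 1.55 | 3.80 |
| 10% | 11.80% | 15.40% | 1.31 | 3.60 |
| 20% | 21.60% | 24.80% | 1.15 | 3.20 |

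Other assumed pairs, for c = 0, 2, 5, 10 and 20%:

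- 2% vs 4%: ratios 2.00, 1.49, 1.28, 1.15, 1.07; difference from 2.0 down to 1.6 points.
- 4% vs 8%: ratios 2.00, 1.66, 1.43, 1.26, 1.14; difference from 4.0 down to 3.2 points.

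In subjects, with the planned 128 per arm, c = 5% and 2% vs 6%: 128 × 0.05 = 6.4 carried-over cases per arm. New cases are 128 × 0.95 × 0.02 = 2.4 and 128 × 0.95 × 0.06 = 7.3. The table would show about 8.8 against 13.7. Among subjects without entry ideation the ratio stays at 3.00.

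**3. Whether the adverse event tables fill the gap.** Event collection opens at consent, so a positive score between consent and first dose can be a pre-dose adverse event. It then becomes the benchmark for its preferred term. The benchmark is the mild/moderate/severe grade, which protocol 10.1.2.2 defines by interference with everyday activities, not by C-SSRS item. A child who moves from item 1 to item 4 at the same grade and preferred term is not a TEAE.

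The number missed per arm is 128 × s × w × m, where s is the share with a pre-dose event, w the share of those who worsen on the C-SSRS, and m the share of worsenings with an unchanged grade. All three are assumed. The low end is 128 × 0.02 × 0.20 × 0.25 = 0.13. A middle case is 128 × 0.05 × 0.50 × 0.50 = 1.6. The high end is 128 × 0.10 × 0.50 × 1 = 6.4.

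**4. Which assessment is baseline.** The Baseline C-SSRS is taken on Day 1, the day of the first dose. SAP 10.0 takes the last value before the first dose, and SAP Table 16.1-1 allows Day 1. SAP 16.3 requires a date before that of the first dose, which read literally falls back to Screening. Any baseline-referenced count needs this settled.

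**The case against.** The strongest reply is that little is lost. Behavior and recent items 3-5 are handled by the entry criteria and shown separately. Randomization balances persisting ideation between arms in expectation. The analysis is descriptive, with no ratio or test planned, and on the absolute scale the difference hardly moves. SAP 16.3 puts all assessments in the listings, so a reader could sort cases by hand. Output specifications are in a separate document that is not available here. All of this stands, and it limits the weight of the point. It does not supply a planned count of new or worsened ideation.

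Three stronger readings are tempting, and the documents do not support them:

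- A reader might infer that neither measure isolates new or worsened suicidality. The TEAE rule in SAP 10.1 counts only events that are new or have increased in severity. Its weakness is masking, which runs opposite to the C-SSRS over-count.
- A reader might infer that protocol 10.1.2.1 conflicts with 10.1.2.2 and makes ideation from years before the trial a TEAE benchmark. The recording rule is qualified by what is appropriate, event collection starts at consent, and psychiatric history is collected separately at Screening. Read together, pre-consent ideation is history.
- A reader might infer that the table is biased toward one arm. Dilution acts on both arms alike.

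Referring on-treatment ideation to the worst category in the previous 6 months would also be a poor remedy. The documents do not show that items 1-2 are recorded for that window, and a recurrence of older ideation would go uncounted.

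**Conclusion.** The point holds as a cheap improvement, confined to low-level ideation. As written, SAP 10.5 cannot distinguish persisting item 1-2 ideation from new onset, and the TEAE tables close only part of that gap. The loss is in interpretability: across the three assumed rate pairs, with 2% to 20% persisting, a true ratio of 2 to 3 is displayed as anything from 1.07 to 1.99, while the absolute difference loses at most a fifth of its value. How far this matters depends on the share entering with item 1-2 ideation, which the documents do not give; if it is near zero, the existing table is adequate. The masking of worsening depends further on how sites record pre-dose positives and on preferred-term coding.

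**What to change.** In SAP 10.5 keep the 'any' row and add, by arm and period:

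- (a) new-onset ideation among subjects with none at the pre-dose assessments;
- (b) worsened ideation, meaning a worst post-dose category above the pre-dose baseline category;
- (c) a shift table from pre-dose baseline to worst post-dose: none, items 1-2, items 3-5, behavior.

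Use the pre-dose C-SSRS actually collected, leaving lifetime answers in their own row. State that the Day 1 pre-dose assessment counts as baseline, and align SAP 16.3 and Table 16.1-1 with that.

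Optionally, add a sentence to protocol 10.1.2.1 that look-back answers about the time before consent are psychiatric history. This would only make explicit what 10.1.2.2 already implies.

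The cost is one SAP paragraph and one more table from scheduled assessments. The new counts will be smaller than the 'any' row and should be read beside it.

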11.0 PHARMACOKINETIC ANALYSIS

PK analysis of Escitalopram will be conducted using a non-linear mixed-effect modeling approach. Population PK parameters, inter-subject, and residual variability will be determined. The effect of covariates on the escitalopram PK will also be investigated. From the developed population PK model (Pop-PK), PK parameters like volume of distribution and clearance will be estimated. Additional PK parameters including, but not limited to, area under the curve at steady-state (AUCSS) will be derived from the individual Bayes estimates from the pop-PK model.

The relationship between efficacy parameters and plasma exposure using a nonlinear mixed effects approach will be explored. The relationship between safety parameters and plasma exposure may also be explored.

A separate analysis plan will be created to detail this approach.

SAP SCT-MD-60 Allergan

Page 38 of 53

12.0 HEALTH OUTCOMES ANALYSES

Not applicable.

SAP SCT-MD-60 Allergan

Page 39 of 53

